4.2.1.2 Exclusion criteria

- 1. Previous carotid stenting or endarterectomy, or stroke;
- 2. Diagnosis of vasculitis, dissection, or non-atherosclerotic carotid disease (Ehlers-Danlos, Marfans);
- 3. Pregnancy or lactation;

Version: 01 Page: **16 of 167**

- 4. History of any disease or relevant physical or psychiatric condition or abnormal physical finding which may interfere with the study objectives at the investigator judgment;
- 5. Know hypersensitivity to the investigational product or any of its components;
- 6. Claustrophobia or inability to lie still in a supine position;
- 7. Participation in another clinical trial within 4 weeks before study inclusion, except for patients who have participated or who are currently participating in a study without any study drug administration:
- 8. Unwillingness to provide consent.

4.2.2 Study exposure

Subjects will be exposed to only one injection of ^{99m}Tc-rhAnnexin V-128 for SPECT/CT imaging of the carotids and aortas.

4.3 Methods and procedures

4.3.1 Source of study population

The carotid artery study population will be adult male and female patients who are referred to the outpatient cardiology clinics and/or the non-invasive Diagnostic Imaging Department at the University of Ottawa Heart Institute. The control population will be healthy volunteers who do not have carotid atherosclerosis as assessed by ultrasounds and whose lab values are within the normal range.

4.3.2 Participants study identification

Each participant will be identified with a participant ID number. A unique participant identification number (Participant ID) will be assigned at the start of the screening period to each participant who signs the informed consent form. This number will identify the participant throughout the study. Participant IDs will include the 2-digit protocol number (04), the 2-letter code (CA) and a 3- digit participant number (ex: 04-CA-001 for first participant in).

4.3.3 Study procedure

Voluntary written informed consent will be obtained prior to the initiation of any study-related procedures. Study conduct procedures will include a screening visit, the imaging studies, a phone visit within 24 hour post ^{99m}Tc-rhAnnexin V-128 administration visit and a visit at 30 days.

Version: 01 Page: **17 of 167**

4.3.3.1 Baseline assessments

- Each participant's date of birth (mm/yyyy), gender, ethnicity, weight, height, medical history, and relevant baseline characteristics will be recorded.
- Results from any standard of care testing related to the participant's condition will be collected.
- Women of childbearing potential must have negative pregnancy test at screening and before the investigational product administration.
- Limited physical exam (height, weight, BMI) and vital signs (systolic and diastolic blood pressure, heart rate), will be recorded.

4.3.3.2 Laboratory assessments

Blood samples for hematology, biochemistry and urinalysis will be obtained at baseline for screening, 30 ± 3 days post IP administration and following any adverse events.

In case of clinically significant abnormalities in baseline laboratory values, the participant will be declared as a screening failure.

Hematology	Coagulation	Blood Chemistry	Urinalysis
WBC with differential RBC Platelets Hb MCV Hematocrit	• PT • PTT • INR	 BUN Uric Acid Albumin Direct bilirubin LDH Calcium Chloride Phosphorus Total cholesterol Total protein Serum creatinine Total bilirubin ALP AST/ASAT ALT/ALAT Gamma-GT Sodium Potassium Glucose β-HCG at screening 	Dipstick test ¹ Pregnancy test (before injection of study product, if applicable)

¹ In case one of the assessments of the dipstick test is positive, a microscopic analysis of the urine must be performed.

Version: 01 Page: **18 of 167**

Laboratory Assessments will be performed by the ■

The Ottawa Hospital according to Ministry of Health and Long Term Care (MHLTC) standards.

To rule out development of anti-annexin V-128 antibodies, venous blood samples will also be drawn for each participant at screening and 30 ± 3 days post ^{99m}Tc-rhAnnexin V-128 injection. Assays for anti-rhAnnexin V-128 IgG and IgM antibodies will be performed in serum samples by ELISA. For this purpose, 10 mL of blood will be collected for each assay.

4.3.3.3 99mTc-rhAnnexin V-128 Planar and SPECT Imaging of the Carotid Arteries and Aorta and Image Analysis

Planar and SPECT imaging of the carotids and aorta will be performed 60 and 120 minutes after injection of tracer.

Administration of the ^{99m}Tc-rhAnnexin V-128 (350 MBq ± 10%) will be as a single bolus via an intravenous catheter in an antecubital vein followed by a saline flush. Negative pregnancy test for women of childbearing potential will be confirmed on the day of administration.

All images will be acquired with a dual head SPECT/CT gamma camera with low-energy high-resolution collimators. The energy acceptance window for the ^{99m}Tc photopeak will be 140 keV (± 10%). A low dose CT scan (helical, 120 kVp, 1 mA with 1.9 pitch) will be acquired of the neck, thorax and abdomen for attenuation correction.

Reconstruction will be done using iterative reconstruction incorporating CT-based attenuation correction and dual-energy-window scatter correction. SPECT images of the carotid arteries and thoracic and abdominal aorta will be acquired at 1 and 2 hours post-injection. Acquired images will be stored for off-line analysis using a Hermes Gold workstation (Hermes Medical Solutions). Volumes-of-interest (VOIs) will be placed over the carotids and the thoracic and abdominal aortic sections to determine image counts from the attenuation and scatter corrected images. A ^{99m}Tc source of known activity will be imaged and used to determine the imaging system calibration factor for converting reconstructed image counts into an activity concentration (MBq/cc or % injected dose/gram).

A normal database of carotid and aortic uptake will be determined from 10 control participants and used to identify abnormal uptake in carotid artery disease participants.

Inter and intra-observer variability will be determined by repeated analysis of the images of 20 participants. Two observers will carry out the assessment of inter-observer variability. Images will be anonymized prior to analysis and observers will be blinded to all clinical data.

4.3.3.4 99mTc-rhAnnexin V-128 Radiation Risk Assessment

Participants will receive radiation from 1) ^{99m}Tc-rhAnnexin V-128 (350 MBq) for a dose of 2.2 mSv (7.7 ± 0.8 uSv/MBq) and 2) the CT scan for attenuation correction for a dose of 1.8 mSv. Total dose for ^{99m}Tc-rhAnnexin V-128 and CT components will be 4.0 mSv.

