4.2.1 Study population

Approval for the study was obtained from the Ottawa Hospital Science Network Research Ethics Board (OHSN-REB) and Health Canada. All participants will provide written informed consent prior to the initiation of any study procedures. Thirty-five participants with carotid stenosis and ten age and sex matched control participants will be enrolled.

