6.1.3.2 Clinical laboratory values

Hematology, blood chemistry, urinalysis and immunogenicity values are recorded at baseline for screening, 30 ± 3 days post IP administration and following any adverse events. Descriptive statistics including shift tables will be generated for all laboratory tests performed i.e. the actual values and the changes from pre-injection.

Data listing will be ordered by subject and measuring time. Listings of abnormal results (both clinically and non-clinically relevant) will also be reported.

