6.1.4 Missing data and outliers

6.1.4.1 Missing data

As stated in the protocol, missing data will not be replaced.

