KETONES			STATISTIC	SCREENING VISIT	VISIT 3
Patient*	Test result	Negative	n (%)	99 (99.9)	99 (99.9)
		Positive	n (%)	99 (99.9)	99 (99.9)
		Not Done	n (%)	99 (99.9)	99 (99.9)
		Missing	n (%)	99 (99.9)	99 (99.9)
	Change from baseline	Missing	n	-	99
		Negative/Negative	n (%)	-	99 (99.9)
		Negative/Positive	n (%)	-	99 (99.9)
		Positive/Negative	n (%)	-	99 (99.9)
		Positive/Positive	n (%)	-	99 (99.9)
Control*	Test result	Negative	n (%)	99 (99.9)	99 (99.9)
		Positive	n (%)	99 (99.9)	99 (99.9)
		Not Done	n (%)	99 (99.9)	99 (99.9)
		Missing	n (%)	99 (99.9)	99 (99.9)
	Change from baseline	Missing	n	-	99
		Negative/Negative	n (%)	-	99 (99.9)
		Negative/Positive	n (%)	-	99 (99.9)
		Positive/Negative	n (%)	-	99 (99.9)
		Positive/Positive	n (%)	-	99 (99.9)

Source: Data listings {Specify data listing number(s)} Analysis dataset: {Specify datasets}

^{*} Patient = Subject with asymptomatic plaque; Control = Healthy volunteer

Version: 01 Page: **149 of 167**

Table 14.3.5.3/7: Urinalysis – RBC (per high power field) – Safety Population

RBC (PER HIGH POWER FIELD)	STATISTIC	SCREENING VISIT	VISIT 3	CHANGE
Patient*	n	99	99	99
	Missing	99	99	99
	Mean	99.9	99.9	99.9
	S.D.	99.9	99.9	99.9
	Median	99.9	99.9	99.9
	Q1, Q3	99.9, 99.9	99.9, 99.9	99.9, 99.9
	Min, Max	99, 99	99, 99	99, 99
Control*	n	99	99	99
	Missing	99	99	99
	Mean	99.9	99.9	99.9
	S.D.	99.9	99.9	99.9
	Median	99.9	99.9	99.9
	Q1, Q3	99.9, 99.9	99.9, 99.9	99.9, 99.9
	Min, Max	99, 99	99, 99	99, 99

Source: Data listings {Specify data listing number(s)} Analysis dataset: {Specify datasets}

^{*} Patient = Subject with asymptomatic plaque; Control = Healthy volunteer

Version: 01 Page: **150 of 167**

Table 14.3.5.3/8: Urinalysis – WBC (per high power field) – Safety Population

WBC (PER HIGH POWER FIELD)	STATISTIC	SCREENING VISIT	VISIT 3	CHANGE
Patient*	n	99	99	99
	Missing	99	99	99
	Mean	99.9	99.9	99.9
	S.D.	99.9	99.9	99.9
	Median	99.9	99.9	99.9
	Q1, Q3	99.9, 99.9	99.9, 99.9	99.9, 99.9
	Min, Max	99, 99	99, 99	99, 99
Control*	n	99	99	99
	Missing	99	99	99
	Mean	99.9	99.9	99.9
	S.D.	99.9	99.9	99.9
	Median	99.9	99.9	99.9
	Q1, Q3	99.9, 99.9	99.9, 99.9	99.9, 99.9
	Min, Max	99, 99	99, 99	99, 99

Source: Data listings {Specify data listing number(s)} Analysis dataset: {Specify datasets}

^{*} Patient = Subject with asymptomatic plaque; Control = Healthy volunteer

Version: 01 Page: **151 of 167**

Table 14.3.5.3/9: Urinalysis – Casts – Safety Population

CASTS			STATISTIC	SCREENING VISIT	VISIT 3

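### Urine microscopy is scheduled only after a positive dipstick, so the change displays in Tables 14.3.5.3/7 to /9 cover only participants positive at both visits

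*SAP*

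**What the plan says.** Urine is tested at two scheduled times: "Blood samples for hematology, biochemistry and urinalysis will be obtained at baseline for screening, 30 ± 3 days post IP administration" (SAP 4.3.3.2), and again after any adverse event. The urinalysis panel lists a dipstick and, where applicable, a pregnancy test. Microscopy enters through a footnote: "In case one of the assessments of the dipstick test is positive, a microscopic analysis of the urine must be performed". Protocol 10.2 carries the same footnote, and neither document schedules microscopy otherwise.

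Three SAP shells report microscopy results:

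- "Table 14.3.5.3/7: Urinalysis – RBC (per high power field) – Safety Population" and "Table 14.3.5.3/8: Urinalysis – WBC (per high power field) – Safety Population" are continuous summaries (n, missing, mean, S.D., median, quartiles, range) in columns for screening, Visit 3 and change.
- Table 14.3.5.3/9 (casts) is categorical. Its test-result block has negative, positive, not-done and missing rows at each visit. Its change-from-baseline block has only a missing row and the four negative/positive pairings.

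On gaps in the data, SAP 6.1.4.1 says: "As stated in the protocol, missing data will not be replaced". No rule gives a value or a category to a participant whose microscopy was not triggered.

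On the type of display, SAP 6.1.3.2 says: "Descriptive statistics including shift tables will be generated for all laboratory tests performed i.e. the actual values and the changes from pre-injection". Protocol 12.5.2 goes further and specifies cross-tabulations classed as below, within and above the normal range. SAP section 8 reports no changes from the protocol.

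**The concern.** A change from screening exists only if the test was done at both visits. Haematology, chemistry and the dipstick itself are scheduled at both visits, so their change columns can in principle cover everyone. Microscopy is different: whether it is done depends on the dipstick result at that visit. Being in the change display is then a consequence of the urine findings that the display is meant to describe.

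The participants of most interest after dosing are those with clean urine at screening and sediment at Day 30. They have a Visit 3 count and no screening count, so no change. The tracer is cleared through the kidneys (protocol section 3), so the urinary sediment is a reasonable place to look. A mean change near zero in a handful of persistently positive people could be read as reassurance about the whole Safety population.

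**Working it through.** The plan states no figure for this point, so there is nothing to reproduce. The check is one of data availability.

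**Step 1. Who has what, under the footnote and without imputation**

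| Screening dipstick | Day 30 dipstick | Screening microscopy | Visit 3 microscopy | Change |
|---|---|---|---|---|
| any item positive | any item positive | yes | yes | yes |
| all negative | any item positive | no | yes | no |
| any item positive | all negative | yes | no | no |
| all negative | all negative | no | no | no |

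The n under change in /7 and /8 therefore equals the number positive at both visits. In /9 the second and third rows fall under missing in the change block. That includes new casts, which do not reach the negative-to-positive row. The screening means come from rows 1 and 3 and the Visit 3 means from rows 1 and 2, so the two columns describe different people.

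**Step 2. Size**

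Inputs:

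- N = 45, from "Thirty-five participants with carotid stenosis and ten age and sex matched control participants will be enrolled" (SAP 4.2.1): 35 + 10.
- The documents give no dipstick rates, so three are assumed: p = share positive at screening (5–30%), q = share newly positive among those negative at screening (2–20%), r = share of screening positives still positive at Day 30 (50–80%).

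Formulas:

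- in the change column = N × p × r
- newly positive, omitted = N × (1 − p) × q
- resolved, omitted = N × p × (1 − r)
- share of Visit 3 microscopy results absent from change = new / (both + new)

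Results:

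- Fewest in change: 45 × 0.05 × 0.5 = 1.1. Most: 45 × 0.30 × 0.8 = 10.8.
- Smallest share absent (p = 30%, q = 2%, r = 80%): new = 45 × 0.70 × 0.02 = 0.63; 0.63 / (10.8 + 0.63) = 6%.
- Largest share absent (p = 5%, q = 20%, r = 50%): new = 45 × 0.95 × 0.20 = 8.55; 8.55 / (1.125 + 8.55) = 88%.
- A middle case (p = 10%, q = 10%, r = 50%): 2.25 in change, 4.05 new and 2.25 resolved omitted; 4.05 / 6.30 = 64% absent.

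**Step 3. What the shell would print, on invented data**

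Take 3 participants positive at both visits with red cells 5 then 5 per field, 6 newly positive with 12 per field at Day 30, and 36 negative throughout.

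- Change column: n = 3, mean 0.0. All six new findings are outside it.
- Screening column: n = 3, mean 5.0. Visit 3 column: n = 9, mean (3 × 5 + 6 × 12) / 9 = 9.7.
- If a negative dipstick is counted as zero cells (an assumption for contrast only), the mean change over 45 is (6 × 12) / 45 = +1.6.

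**Step 4. Which other displays show a new finding**

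- Red cells: Table 14.3.5.3/1 gives negative-to-positive shifts for dipstick blood.
- White cells: no dipstick leukocyte table exists, so there is no shift display.
- Casts: the shift rows in /9 exist, but a participant without screening microscopy cannot be placed in them.

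**The case against.** The best case against is that little is actually hidden. Every new Visit 3 count enters the Visit 3 column of /7 or /8, where the maximum would show a high value. New casts are counted in the Visit 3 positive row of /9. Individual results are in Listing 16.2.8.3, abnormal results are listed whether or not clinically relevant (SAP 6.1.3.2), and clinically significant ones go to Table 14.3.4. Dipstick blood and protein have shift rows, and urea nitrogen and creatinine have change tables from tests scheduled at both visits. The shells print n and missing under change, so a very small n is disclosed. Safety analysis is mainly descriptive and no decision uses these cells. All of this stands, and it keeps the point minor.

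It also rules out three stronger readings that a reader might infer:

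- *The sediment tables cannot show a post-dose signal.* The Visit 3 columns can; the loss is confined to the change displays.
- *No new red- or white-cell finding can enter the change column.* Any positive dipstick item triggers microscopy. Someone positive for glucose at screening has counts at that visit, so a new finding at Day 30 does enter.
- *The change column is biased towards safety.* Resolved findings drop out too, so the direction is not fixed.

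That microscopy is done *only* on a trigger is an inference. The footnote requires it after a positive dipstick and does not forbid it otherwise; the eCRF and local laboratory practice are not visible. But nothing else schedules it.

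The objection does not rescue the change summaries themselves. A printed missing count does not separate *not required* from *not obtained*. The not-done row in /9 could do so at each visit, but its change block has no such level. Comparing the screening and Visit 3 columns does not help, because they describe different people.

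**Conclusion.** The point holds for the change columns of /7 and /8 and the change block of /9. As written, they summarise only participants with a positive dipstick, on any item, at both visits. New sediment after a wholly negative screening dipstick is left out, and so is resolution. New white cells and casts then have no working shift display.

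The size is uncertain: about 1 to 11 of 45 participants in the change column, and about 6% to 88% of Visit 3 microscopy results absent from it. These ranges rest on the assumed rates and on microscopy being done only when triggered. Two provisions could push the number lower. The first is the rule "In case of clinically significant abnormalities in baseline laboratory values, the participant will be declared as a screening failure". The second is the requirement that controls have laboratory values in the normal range (protocol 8.3, SAP 4.3.1); if it covers urinalysis, the control change column would be nearly empty.

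Severity is low. This is a descriptive safety display, and no efficacy endpoint is affected.

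**What to change.** Replace the change summaries in /7 and /8 and the change block in /9 with screening-to-Visit 3 shift tables, which protocol 12.5.2 and SAP 6.1.3.2 already promise. Use four levels at each visit:

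- dipstick negative, microscopy not required
- microscopy within normal range
- microscopy above range, or casts present
- missing

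Use the Safety population, by group, as denominator, so that every dosed participant appears once. Keep individual counts in Listing 16.2.8.3. If the screening and Visit 3 summaries stay in /7 and /8, footnote that they cover only participants with microscopy at that visit and should not be compared. A footnote on the change denominator alone would disclose the selection but not show the new findings.

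The cost is three table shells and one derivation rule for the *not required* level. No new data and no change in study conduct are needed.

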4.3.3.5 Ultrasound Examination

Clinical evidence of 50% or more carotid stenosis in one or more carotid arteries on carotid ultrasound within 10 years prior to enrolment is required for inclusion in the trial.

Evidence of 50% or more carotid stenosis has to be confirmed in a more recent US imaging within 8 weeks prior to ^{99m}Tc-rhAnnexin V-128 administration. If not confirmed, the participant will be declared as a screening failure.

B-mode and color Doppler ultrasound studies will be acquired of both carotid arteries and performed with an ultrasound scanner equipped with a 5- to 7-MHz transducer. Plaque morphology, as echogenicity, defined as reflectance of the emitted ultrasound signal, will be assessed as previously described and graded from 1 to 4 as echolucent, predominantly echolucent, predominantly echogenic, or echogenic. The vessel lumen will be used as the reference structure for defining echolucency, and the bright echo zone produced by the media-adventitia interface in the far wall will be used as the reference structure for defining echogenicity. Interobserver reproducibility of plaque morphology in stenotic arteries has been previously assessed (κ =0.56, 95% C.I. 0.38 to 0.74).

The degree of stenosis will be calculated by the following equation: (1-PSVr/PSVs)×100%, where PSVr denotes peak systolic velocity at the point of reference (here, the distal carotid artery) and PSVs the peak systolic velocity in the stenosis.

4.3.3.6 Withdrawal/discontinuation

The withdrawal of a study participant is mandatory in the following cases:

- Pregnancy
- Protocol violation determined as critical
- Lost to follow-up
- Serious inter-current illness or other safety reasons for what the Investigator considers it is in the best interest of the participant to withdraw from the study
- Screening failure

A "screening failure" is a participant who has signed the informed consent, but who does not meet all selection criteria following the screening evaluations. For participants not considered eligible after the screening period, the reason for not being eligible must be documented. No additional assessments are needed. Participant information collected at the screening visit will be entered in the eCRF and will be used in the study analysis.

The participants may withdraw from the study if they decide to do so, at any time and irrespective of the reason, or this may be the Investigator's decision. The primary reason for a participant's withdrawal from the study should be determined if possible. The date and reason for discontinuation will be documented in the eCRF.

4.3.4 Schedule of assessments

Participants who have signed the informed consent and are eligible to participate in the study will undergo the following assessments:

- A screening visit will be conducted within 8 weeks prior to the ^{99m}Tc-rhAnnexin V-128 imaging. Eligible and consenting participants will undergo a limited physical examination (height, weight, BMI), vital signs (systolic and diastolic blood pressure, heart rate), blood analysis and urinalysis. The following blood analysis will be conducted: CBC with automated differential, general chemistry panel (SMA-20) including PT/PTT, INR (international normalized ratio for PT values) and assessment of anti-annexin V-128 antibodies.
- Carotid ultrasound will be carried out within 8 weeks prior to the ^{99m}Tc-rhAnnexin V-128 SPECT/CT imaging. SPECT Imaging visit: dedicated SPECT/CT imaging of the carotids and aorta will be done 60 minutes after injection of tracer, and 120 minutes after injection. Vital signs assessment/participant monitoring will be done throughout the visit.
- Within 24 hours after the administration of ^{99m}Tc-rhAnnexin V-128, participants will be called for the assessment of possible adverse events.
- 30 ± 3 days post ^{99m}Tc-rhAnnexin V-128 injection, all participants will return to clinic for a final blood sampling to rule out the development of anti-annexin V-128 antibodies. The following blood analysis will also be conducted: CBC with automated differential, general chemistry panel (SMA-20) including PT/PTT, and INR.
- Once the first 15 patients and 5 normals have been administered with ^{99m}Tc-rhAnnexin V-128 and have performed the imaging visits, the Data Monitoring Committee will review the images. The visual assessment of the scans in these first 20 participants will support the continuation or the termination of the Phase II study.

Version: 01 Page: **21 of 167**

The following table summarizes all the procedures and evaluations to be conducted during the study:

Study Procedures	Screening (Within 8 weeks prior to Day 0)	SPECT/CT Visit (Day 0)	24 hours post IP injection ¹	30 ± 3 days post IP injection (Day 30)
Written informed consent	X			
Inclusion/exclusion criteria	X	X		
Medical history	Х			
Concomitant medications	Х	X	Χ	X
Physical examination (height, weight, BMI)	Х	х		
Vital signs (BP, HR)	×	×		
Lab analysis (hematology, PT/PTT/INR, biochemistry, urine)	×			Х
Immunogenicity by ELISA ²	Х			Х
Pregnancy test	Х	X		
Carotid ultrasound ³	Х			
rh-Annexin V-128 administration		Х		
Planar & SPECT/CT imaging		Х		
Adverse events assessment		Х	Х	Х

¹Within 24 hours after injection of ^{99m}Tc-rhAnnexin V-128, each participant will be called to review any signs or symptoms of AEs.

